4.2 SCIENTIFIC RATIONALE FOR STUDY DESIGN

We propose a parallel, randomized controlled trial (RCT) as the most scientifically robust design to determine the efficacy of HEPA filtration in improving the number of SFD over 24 weeks following hospitalization for bronchiolitis. We

Title: *The BREATHE Study: Bronchiolitis Recovery and the Use of High Efficiency Particulate Air (HEPA) Filters*

Sponsor: ISPCTN DCOC

considered two alternative study designs to increase acceptability of an inactive filtration unit: randomized crossover and stepped wedge. Parallel, crossover, and stepped wedge designs each allow for a control or placebo group, which is critical as there is genuine uncertainty regarding the efficacy of the intervention in reducing SFDs in the 6 months following hospitalization for bronchiolitis. The parallel design is distinct from the other two in that homes randomized to the control arm will not receive the intervention during follow-up.

Both the crossover and stepped wedge designs are appealing in that they allow all participants to receive an intervention that we expect will improve IAQ. However, with a crossover design, it is critical that the participant's disease characteristics are the same at time zero of each time period. Since the eligibility for this study is based on hospitalization for bronchiolitis, there is no way that can be achieved. Moreover, the relevant time window of exposure, washout duration, and appropriate point in time to crossover is unclear. Although an early benefit of HEPA filtration is possible, the intervention may be more effective over a longer duration rather than the immediate period post-hospitalization, which would require a lengthy study.

The stepped wedge is a variant of an interrupted time series design in that a site starts in the control arm and switches over to the intervention arm at a specific point in time. While participants may be blinded, staff are not, so this might be difficult to implement.

We considered a 1-year study intervention period. However, due to family burden, risk of missing data, and risk of nonadherence to the intervention over such a long duration, we ultimately decided that a 24-week intervention targeting the time period of highest respiratory burden was preferable. Although a 1-year study period is appealing due to capturing potential variability in air quality (heating season, etc.) and viral exposures (cold seasons), the severity of respiratory symptoms is not static in rapidly growing infants, and most of these children will be recruited in the same seasons and have similar opportunity for repeat viral exposures and heating seasons between the groups.

We considered including children up to 2 years of age (per the definition of bronchiolitis). However, the under 12-months age group has the highest symptom burden and likelihood of demonstrating an effect.

We chose the primary outcome of symptom-free days because assessing the number of wheezing episodes alone can underestimate the burden of chronic symptoms (including cough) and prolonged symptoms with illness episodes. In addition, clinically it can be difficult to determine the discrete number of wheezing episodes for children with prolonged or chronic wheeze (which is a higher risk in this population).

The KidsAir study at the ISPCTN Montana site successfully implemented and completed a study similar in design to the one we propose here.⁸⁵ The proposed study benefits from methods used in the KidsAir study, lessons learned, and the study team's expertise. Although the current study population is different from that of the KidsAIR study, the KidsAIR study targeted for intervention the same exposure to PM_{2.5} as the current study using the same method, namely HEPA filtration, and collected similar covariate data successfully over two winters of study participation.⁸⁶ In the KidsAIR study, field technicians visited homes approximately six times per winter season. Data collection procedures were more burdensome for participants and more frequent than those proposed here (see Schedule of Activities, Section 1.3); however, participant retention in the other study was still 87% in the first year of the 2-year KidsAIR study. The current study requires a relatively shorter duration of study participation (6 months versus 2 years) and less burdensome procedures for outcome ascertainment that do not require participating families to accommodate home visits by field technicians.

4.3 JUSTIFICATION FOR DOSE

The HEPA unit intervention will take place over the approximately 6 months after hospitalization because this period is when the majority of post-bronchiolitis respiratory symptoms occur.^{5,26,31} The intervention involves the placement of two HEPA units within the home. The rationale for the placement of one HEPA unit in the child's sleep space is that infants typically spend a continuous number of hours daily in this space. The rationale for placement of a second HEPA unit in a common area of the home is to increase the child's exposure to the intervention during waking hours.

4.4 END OF STUDY DEFINITION

An individual participant will be considered to have completed the study after completing all final protocol-specified assessments at the end of the 24 week intervention period (which is equal to week 26 in SOA due to approx. 2 week pre-intervention period). Participants will be considered not to have completed the study if consent was withdrawn or the subject was lost to follow-up without submitting all end-of-study questionnaires (at end of 24 weeks of intervention) and surveys. The end of study (“study completion”) is defined as the date the last protocol-specified visit/assessment (including telephone contact and receipt of questionnaires and surveys) is completed for the last participant in the study. Scheduled study activities are shown in the Schedule of Activities (SOA), Section 1.3.

5 STUDY POPULATION

5.1 INCLUSION CRITERIA

To be eligible to participate in this study, an individual child must meet all of the following criteria:

- Age <12 months at hospital admission
- First-time hospitalization for bronchiolitis
- One primary residence (≥ 5 days per week)
- Parent, legal guardian or other legally authorized representative consents to allow their child to participate and agrees to participate in all study activities
- Electricity in the home (required to power the study equipment)
- Wireless internet access or cellular service access in the home*
- English or Spanish-speaking parent or guardian

*Cellular service allows the study-provided hotspot to transmit PurpleAir monitor data and study surveys.

5.2 EXCLUSION CRITERIA

An individual child who meets any of the following criteria will be excluded from participation in this study:

- Chronic airway or respiratory conditions requiring home oxygen, mechanical ventilation, or tracheostomy dependence; known immunodeficiency, hemodynamically significant cardiac conditions including those requiring medication or oxygen; cystic fibrosis; neuromuscular disease; eligible for palivizumab (per AAP guidelines⁸⁷)
- Use of stand-alone home HEPA filtration other than study-related HEPA units in the home
- Household member who smokes (any type), vapes, or uses e-cigarettes
- Intention to move in the next 6 months
- Enrolled or plans to enroll in an interventional clinical trial for treatment of acute bronchiolitis or sequelae of bronchiolitis, unless permission given by the PI
- Another child in the household is enrolled in this study (one child per household can enroll)

We will exclude homes with smokers to maximize our ability to determine the efficacy of the HEPA intervention in increasing SFDs. Multiple studies have demonstrated efficacy of HEPA filtration units in reducing non-nicotine particle-bound components of tobacco smoke.^{67,72,88-90} However, we propose to exclude households with a smoker because even if HEPA filtration units reduce tobacco smoke components in the home, the secondhand smoke (SHS) exposures the child experiences with the smoker outside of the home (e.g., in the car) may be sufficient to reduce or eliminate any health benefits of the indoor HEPA unit. A systematic review and meta-analysis of 60 studies showed that passive smoke

Title: *The BREATHE Study: Bronchiolitis Recovery and the Use of High Efficiency Particulate Air (HEPA) Filters*

Sponsor: ISCPTN DCOC

exposure is a major risk factor for lower respiratory tract infections and, in particular, bronchiolitis,⁹¹ as well as increased respiratory symptoms.⁹² In addition, infants who live with a smoker may be exposed to more sources of SHS.⁹³ The exclusion of homes with smokers is consistent with the majority of RCTs that have evaluated the impact of portable air cleaners on health.²²

We acknowledge that excluding children living in households with a smoker will reduce the number of eligible participants. Nonetheless, including children from households with a smoker may increase sample size requirements if the intervention is less efficacious in smoking households.^{72,94} We emphasize that the proposed trial is an efficacy study. Our primary objective is to determine if HEPA filtration increases SFDs in children hospitalized for bronchiolitis under ideal circumstances. There is genuine uncertainty regarding this research question. Although smoking may be more prevalent in IDeA states, the percentage of homes with children and non-smokers is still clearly the majority, making the study still generalizable to a very large population of children with bronchiolitis.

If the intervention is efficacious, a next step would be to evaluate if these findings are generalizable to other populations, including children living in households with a smoker.

No children receiving concomitant medical therapies will be excluded.

5.3 LIFESTYLE CONSIDERATIONS

Not applicable.

5.4 SCREEN FAILURES

A screen failure is a participant who, upon initial evaluation potentially meets inclusion criteria (e.g., through chart review, etc.) and does not appear to have any exclusion criteria, but who, upon further evaluation (e.g., discussion with parent(s)/guardian(s) about whether there is electricity in the house, whether anyone in the house smokes, whether they plan on moving within 6 months, etc.) prior to enrollment/randomization, does not meet either all of the inclusion criteria and/or has 1 or more exclusion criteria. Screen failure information will be collected and recorded on the appropriate case report form (CRF) and will include all reasons for the failure.

Individuals who do not meet the criteria for participation in this trial (screen failure) because of a modifiable factor may be rescreened. Rescreened participants should be assigned the same participant number as for the initial screening.

5.5 STRATEGIES FOR RECRUITMENT AND RETENTION

Recruitment and retention of eligible participants will be critical to study success. Within a multi-center network, optimal recruitment approaches may vary from site to site, and network success may require sharing best practices among clinical sites. Though each clinical site is responsible for recruiting, enrolling, and retaining study participants, the Data Coordinating and Operations Center (DCOC) will assist each site in creating a site-specific recruitment and retention plan. Site initiation visits will include a review of the individual site's recruitment and retention plans. All recruitment and retention materials, general and site-specific, must be approved by the IRB of record, which for all sites except Native American sites, will be the UAMS IRB.

Screening/Recruitment:

Eligible children will be identified during a primary hospitalization for bronchiolitis. We will request a partial waiver of consent consent/HIPAA for the recruitment screening portion of the study, i.e., to allow sites to review medical records for potentially eligible participants that meet minimum inclusion criteria. This partial waiver will be required to reach the appropriate study population.

Title: *The BREATHE Study: Bronchiolitis Recovery and the Use of High Efficiency Particulate Air (HEPA) Filters*

Sponsor: ISPCTN DCOC

Screening. Local sites will obtain a daily list or receive notification of admissions to their pediatric units with a diagnosis of bronchiolitis (of the days where the research team is available). This information will be obtained in accordance with individual institutional policies and procedures as well as IRB approval from the IRB of record. For non-Native American populations, the UAMS IRB (as central IRB), will be the IRB of record.

Recruitment. Each potential participant on the list should be approached for recruitment if the child meets eligibility criteria from prescreening their medical record. Recruitment can occur in person or remotely in accordance with institutional requirements, family preference, and healthcare team approval. Remote consent must be done according to the requirements specified in section 10.

Screening and enrollment ideally will occur during hospitalization, but enrollment can occur after discharge to home *if the family can receive and set-up the air quality monitoring equipment within 7 days of discharge*. Other procedures can occur at home. **Day of hospital discharge is defined as day 1.**

If an eligible child is readmitted within 1 week of discharge to home from the initial hospitalization, this can be considered part of the same hospitalization and timeframe to obtain the consent (if not already done). The start of study activities resets to begin after the second discharge to home.

If a potential participant appears to meet eligibility requirements (i.e., based on pre- screening assessment) but declines participation, the parent(s)/legal guardian(s) will be asked why they do not want to participate. These data will be recorded in a screening log without any identifiers that could link responses back to an individual or family. The individual/family will be told they do not have to answer any questions they do not want to answer.

Action if recruitment is low/risk mitigation plan: Methods for screening and recruitment at individual sites will be reviewed to determine if there are gaps in offering the study or other factors leading to low recruitment. Sites will submit recruitment data (number of bronchiolitis admissions, number approached, number consented, reason for declining the study) to the DCOC every 2 weeks. Individual site action plans may be made to improve recruitment.

Using data from nine ISPCTN sites, we observed 3,209 admissions for bronchiolitis in infants less than 12 months of age during the 2019-2020 season. We estimate that we will have a minimum of 10-14 sites in this trial. Therefore, we will have a population of approximately 3,500-5,000 infants hospitalized from bronchiolitis to recruit from per year. Given that the recruitment period for this study is estimated at 2 years, we should have 7,000-10,000 eligible infants during the study period in our recruitment sites. Assuming a conservative recruitment rate of 20% would give us 700-1,000 infants, which is far greater than the recruitment targets for this trial. Additional sites could be added to the trial if recruitment falls short, as the ISPCTN has 18 awardees, some with multiple available recruitment sites.

Consent:

The consent process will be conducted as described in section 10 of this protocol.

Retention/Incentives:

Some studies reported decreased HEPA filtration unit usage over the course of follow-up.^{70,95} Study participants indicated noise and electricity costs as reasons for turning off the filtration unit or using it below the recommended setting. To address these challenges, we selected a filtration unit model that emits low decibels and has low electricity demands. A similar unit was used in the KidsAIR study. Evaluation of Kilowatt (kW) meter data in KidsAIR indicated strong compliance with filtration unit usage recommendations. In addition, we will compensate participating families for electricity costs. Our intervention period of 6 months is favorable for adherence relative to a year(s)-long intervention. Additionally, coordinator contacts will provide problem-solving strategies and support for continued use of the HEPA filtration unit.

Coordinator contact for engagement while collecting study data: The research coordinator or other qualified research team member will check in with the family periodically. Check-in will typically be via phone call, but if permitted locally contact may occur by other means (such as text, email, video conferencing).

Title: *The BREATHE Study: Bronchiolitis Recovery and the Use of High Efficiency Particulate Air (HEPA) Filters*

Sponsor: ISCPTN DCOC

Weeks 1-4: Check-in: Contact from the enrolling site:

- Weekly and as needed check-in: (Site to conduct a weekly check-in at a minimum)
- Assist or prompt EDC documentation as needed
- Assess equipment set-up, questions/concerns
- Safety assessments (AE, SAE, UPIRTSO)
- RSV vaccination/preventive treatment status may be collected as appropriate

Weeks 5-26: Check-in: Contact from the enrolling site:

- Monthly and as needed: (Site and participant dependent)
- Assist or prompt EDC documentation as needed
- Assess equipment questions/concerns
- Safety assessments (AE, SAE, UPIRTSO)
- RSV vaccination/preventive treatment status to be collected as appropriate

Compensation will be provided for completion of study activities

- Weekly survey collection (26 submissions) – \$20 per survey submitted (max \$520 per participant)
- \$10 for submitting QOL survey
- \$5 each for baseline and 6-month (approx. week 26 of participation; week 24 of intervention) history question set (max \$10)
- \$40 for return of the PurpleAir monitors with internal SD cards, hotspot, and kW meter. This is for time spent returning equipment. Parent(s)/guardians of participant will receive pre-paid materials for returning equipment, i.e., at no expense to parent/guardian.

Compensation will be provided for anticipated excess energy costs

- \$15 per family (The anticipated excess energy cost is approximately \$5 per HEPA unit in higher energy cost areas. The \$15 compensation will account for unanticipated energy costs.)

Healthy Homes Kit: All participants will receive a Healthy Homes Kit (approximately \$42.00 value) near the start of their child's study intervention period. The kit contains a collection of items to improve non-IAQ home environmental health and safety. The Healthy Homes Kit is a response to community and stakeholder feedback requesting meaningful home environmental tools in all study arms to make the study more acceptable. We do not expect an impact on the measured outcomes. The rationale for using the Healthy Homes Kit is that the home environment is generally considered important for overall health. The Kit addresses the following concerns: 1) recruitment and retention may be affected with a "placebo only" arm, and 2) when introduced to the rationale that a healthy home environment helps improve health, some families may want to pursue home environment modifications, and the kit will provide standard tools. The kit will contain children's books, outlet covers, doorknob covers, cabinet and drawer latches, bath thermometer, carbon monoxide detector, bedbug traps, and green cleaning supplies.

Additional incentive at study completion and equipment retained by families: All families will retain the two HEPA units (value of \$500) and receive a supply of two HEPA and carbon filters (value of \$160). They also will keep the tape measure (value of \$15), four surge protector power cords (value of \$10 each) and one USB/AC power adapter (value of \$4). They will keep their backpack (valued at approx. \$22).

Compensation Summary:

- **Total possible compensation (reimbursement for time & equipment return) for study activities: \$580**
- **Compensation for excess energy costs: \$15.**
- **Value (approx.) of equipment and supplies that families keep: \$ 806.**

Grand sum value of compensation is, therefore, approximately \$1378.

Return of Results: Indoor air quality results (PM_{2.5}) typically will not be provided to caregivers until after their child's participation has ended (i.e., after 6 months, or sooner if the child's participation ends early). After a participant completes the study, study staff will then send the participant's caregiver a summary of the data from the PurpleAir monitor(s) in their home. Exception: Quality control monitoring will occur during the first 4 weeks (approximately) of study participation. If persistently high air pollutant levels are noticed during those 4 weeks (approx.), participants will be notified as soon as practicable. Note that quality control monitoring can only be done for those households that can transmit their air quality data (PurpleAir data) through wireless methods. For equity, after a participant completes the study and air quality results are assembled based on returned PurpleAir monitors and/or data transmitted through WiFi, the study team will notify the participant's caregiver should persistently high air pollutant levels be noticed.

Once the entire study is completed, study staff will provide a lay summary of the overall study results to caregivers of participants.

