1.2 SCHEMA

During hospitalization

- Total n=228
- Screen potential participants by inclusion and exclusion criteria
- Informed consent (study enrollment)
- Review and document baseline characteristics and risk factors for recurrent wheeze
- Equipment package sent home with family at discharge (air quality measurement equipment) (mailing or locally arranged pickup/delivery are other options)

Pre-intervention (Weeks 1-2 After Hospital Discharge)

- HEPA units mailed to participants
- Pre-intervention measurements: continuous PM_{2.5} measured by PurpleAir monitors in child's sleep space and a common room (family set up of equipment with remote support from the research team)
- Weekly collection of symptoms, healthcare visits, time away from home, and equipment use via EDC survey
- Severe AE, SAE, and UP/UPIRTSO review

Intervention (Weeks 3-26)

- Continuous HEPA unit use (active or control) in child's sleep space and a common room
- Continuous use of kilowatt hour meter to measure HEPA unit adherence
- Continuous PM_{2.5} monitoring via PurpleAir monitor in child's sleep space and a common room
- Weekly collection of symptoms, healthcare visits, time away from home, and equipment use via EDC system
- Severe AEs, SAEs, and UP/UPIRTSOs review

Intervention Week 26

- Quality of Life Survey
- Review and update participant characteristics and risk factors for recurrent wheeze

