⁶ Weeks 1-4, check-in with the enrolling site will occur weekly and as needed (minimum of weekly). Weeks 5-26, check-in with the enrolling site will occur weekly or monthly and as needed (minimum of monthly). During the check-in, the study team will assist or prompt EDC documentation as needed, assess equipment questions/concerns, and safety assessments will occur (AE, SAE, UPIRTSO). Data capture of RSV vaccination/preventive treatment status will be collected by caregiver report or may be obtained from the medical record.

⁷ Family will receive an Electronic Data Capture (EDC) system survey link weekly by text (if allowed by the local site) or email. The family will submit the brief questionnaire (alternatively, the study staff can call the parent(s)/guardian(s) to read the questions and record the responses in the EDC system for the parent(s)/guardian(s)). QOL survey will also be administered electronically (with alternative of survey completion by phone with study staff).

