2.3 RISK/BENEFIT ASSESSMENT

2.3.1 KNOWN POTENTIAL RISKS

This study poses minimal risk to participants. Possible risks include the following:

- There is potential for false reassurance that the intervention prevents all adverse home environmental exposures.
- Noise produced by the device may be considered by some to be a “white noise” but could be bothersome or harmful if the highest setting is used continuously in close proximity to the child.
- The device may take up space, causing inconvenience.
- Participating individuals could be injured or experience electrical shock during instrument installation or use in the home (childproofing required).

Methods of reducing risk are discussed in Section 2.3.3.

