The parent(s)/guardian(s) will submit a brief weekly online survey (via the EDC platform) that they receive via text or email. The alternative is a scheduled phone call with a standard script with the study coordinator or other qualified personnel from the study site research team. Parent(s)/guardian(s) of participants will receive a text or email reminder to complete the survey if it is not completed within 1 day of original due date. If a survey remains incomplete, the research team will continue to provide reminders to the parent/guardian until it is completed or closed.

The weekly survey will capture 4 elements: 1) the child's symptoms for the week, 2) number of healthcare visits, 3) time away from home, 4) study equipment use.

Each family will receive a visual tool (paper form named "Symptom Recall Tool") with the written questions as a prompt/reminder of what will be asked. The family will receive a booklet with a page of the Symptom Recall Tool for each week of the study. The Symptom Recall Tool is an aid for reporting and will not be collected. We estimate that the weekly survey will take 1-5 minutes to complete electronically.

- **Symptom survey:** The survey captures three daytime symptoms (cough, wheeze, trouble breathing) and nighttime awakenings due to cough. The responses to the symptom survey in the EDC will be used to determine SFDs. The questions have been used previously to measure SFDs after bronchiolitis over a similar time frame of approximately 6 months in a study testing whether an intervention reduces post-bronchiolitis symptomatic days.⁵

The questions are based on the Bronchiolitis Caregiver Diary, a validated measurement tool for respiratory symptoms after acute bronchiolitis.³⁷ These questions have been used to follow post-bronchiolitis symptoms over a 20-week period, similar to this study.⁵

- The survey will ask whether the child had any cough, wheeze, or trouble breathing this week (Y/N).
 - If No, they will move on to the next section for healthcare visits.
 - If Yes, they will receive a prompt for each day to respond Y/N for the presence of the symptom and if there are symptoms present, the survey will ask if any medications were used for respiratory symptoms (family to list names of medications).

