8.3 ADVERSE EVENTS AND SERIOUS ADVERSE EVENTS

8.3.1 DEFINITION OF ADVERSE EVENTS (AE)

An AE is any untoward or unfavorable medical occurrence in a human subject, including any abnormal sign, symptom, or disease, temporally associated with the volunteer's participation in research, whether or not it is considered related to the research intervention. Stable chronic conditions that are present prior to enrollment and do not worsen are not considered AEs and will be accounted for in the subject's medical history. Exacerbation or worsening of pre-existing conditions are defined as AEs. Each AE will be classified by the investigator as serious (SAE) or nonserious. All AEs will be evaluated for severity, action taken, seriousness, outcome, and relationship to the study intervention. Information on protocol-specific AEs, severe AEs, and SAEs will be collected from participant reports and via phone calls, as well as review of weekly surveys. Protocol-specific AEs, severe AEs and SAEs will be collected for the duration of the study. We will only record and track severe AEs; SAEs; and AEs associated with the study intervention and/or study equipment.

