8.4.2 UNANTICIPATED PROBLEM REPORTING

The investigator will report UPS (UPIRTSOS) – and potential UPIRTSOS - to the DCOC (who will in turn report to the reviewing IRB when the reviewing IRB is UAMS) and the local IRB as well as any other persons or groups noted in the DSMB charter. Reports to NIH and the DSMB will be made by following the chain of notification.

These problems must be reported to the reviewing/local IRBs according to the reviewing/local IRB's contemporaneous policies and procedures.

For most sites involved in the study, the reviewing IRB will be the University of Arkansas for Medical Sciences (UAMS) IRB. The UAMS IRB contemporaneous policy, 10.2., *Events that must be reported to the IRB and IRB Actions* (effective July 6, 2020) is available via <https://irb.uams.edu/irb-policies/current-irb-policies/>

As of the writing of this section of the protocol (03/23/2022), UAMS IRB reporting requirement per policy 10.2 are:

UPIRTSO Reporting Requirement	
Unanticipated Problem	Required Reporting Time to UAMS IRB
Death or life-threatening	Immediately to IRB office or IRB Chair
All other events	Within 10 days of event or notification of event if non-local

Reports typically require the following information:

- Protocol identifying information: protocol title and number, PI's name, and the IRB project number
- Event date
- Event location
- Nature of the risk
- How the risk relates to research
- A detailed description of the event, incident, experience, or outcome
- A description of any changes to the protocol or other corrective actions that have been taken or are proposed in response to the UP

Examples of UPs/UPIRTSOS that are not an AE or SAE, but which would need to be reported include:

- Breach of confidentiality
- Manufacturer recall of equipment used in the protocol

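### From week 5 scheduled safety questioning has only a monthly minimum, and the weekly survey, as described, has no item for equipment harm or non-respiratory hospital stays

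*Protocol*

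**What the plan says.** Section 5.5 of the protocol gives two phases of site check-ins. For weeks 1-4 the entry is "Weekly and as needed check-in: (Site to conduct a weekly check-in at a minimum". For weeks 5-26 it is "Monthly and as needed: (Site and participant dependent". Both lists include safety assessment for AEs, SAEs and UPIRTSOs. Footnote 6 of the Schedule of Activities (1.3) words the later phase differently: "Weeks 5-26, check-in with the enrolling site will occur weekly or monthly and as needed (minimum of monthly". Footnote 6 in SAP 3.3 follows the Schedule's version.

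Under 8.3.4, families are asked about potentially related AEs, severe AEs and SAEs at study visits or interval calls. Section 6.2.4 requires no in-person visits, so the check-in is in effect the scheduled occasion for those questions.

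Section 8.3.1 says that AE information is "collected from participant reports and via phone calls, as well as review of weekly surveys". It limits recording to severe AEs, SAEs and AEs associated with the intervention or study equipment. Section 8.3.2 makes an inpatient hospitalization an SAE whatever its cause.

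On the survey, 8.1 says: "The weekly survey will capture 4 elements". These are symptoms, healthcare visits, time away from home and equipment use. The visit counts are for respiratory symptoms. The equipment items cover whether each unit was used, its usual setting, the kW reading, and whether the monitor and hotspot lights are on.

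Among the known risks, 2.3.1 lists that participating individuals "could be injured or experience electrical shock during instrument installation or use in the home". The UPIRTSO table in 8.4.2 requires immediate reporting of fatal or life-threatening problems and, for all others, "Within 10 days of event or notification of event if non-local".

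**The concern.** Section 8.3.1 gives the weekly survey a safety task that the survey described in 8.1 cannot fully perform. Two of the classes that the protocol undertakes to record fall through: AEs associated with the equipment, and hospital stays for a non-respiratory reason, which are SAEs by definition. From week 5 the only scheduled prompt for them is a check-in that may come once a month.

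Families install and run the equipment themselves, and staff normally do not enter the home. An event that nobody asks about may be learned of late, or not at all if it was minor and has been forgotten. Late news of a fault in one home delays any action in other homes using the same model. Missed events also thin the AE summaries planned in protocol 9.4.4 and SAP 6.7.

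**Working it through.** The plan states no detection delay of its own, so there is no figure to reproduce. The check has three parts.

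**Weeks affected.** The Schema (1.2) gives "Intervention (Weeks 3-26".
- Intervention weeks: 26 - 3 + 1 = 24
- Weeks 5-26: 26 - 5 + 1 = 22
- Share with only a monthly minimum: 22/24 = 91.7%

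**What the described survey would show.**

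| Event | Nearest item in 8.1 | Captured? |
|---|---|---|
| Injury or shock from a unit, monitor or cord | Unit used, and setting | No; a No on use might hint at it |
| Fault in a unit | Unit used; kW reading | Not asked; only a stopped unit might show |
| Non-respiratory hospital stay | Visit counts for respiratory symptoms | No, on the plain reading |
| Respiratory hospital stay | Same item | Yes |

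**Age of an event when first asked about.** Assume that events fall evenly over a gap of G days between check-ins and are first learned of at the next one. The 10-day mark is used here only as a yardstick.

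P(more than 10 days old) = (G - 10)/G; mean delay = G/2

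| G (days) | More than 10 days old, weeks 5-26 | Mean delay (days) | Over all 24 weeks (x 22/24) |
|---|---|---|---|
| 28 | 18/28 = 64.3% | 14 | 58.9% |
| 30 | 20/30 = 66.7% | 15 | 61.1% |
| 31 | 21/31 = 67.7% | 15.5 | 62.1% |

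The last column gives zero to weeks 3-4, where contact is at least weekly.

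Now let a share s be volunteered within 10 days. The late share becomes (1 - s)(G - 10)/G. The documents give no value for s, so a range is needed:
- s = 0: 64.3% to 67.7%
- s = 0.25: 48.2% to 50.8%
- s = 0.50: 32.1% to 33.9%
- s = 0.80: 12.9% to 13.5%

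The late share is 50% or less once s reaches 1 - 0.5/0.643 = 22% (G = 28) to 1 - 0.5/0.677 = 26% (G = 31).

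**With a weekly item.** SAP 6.6.1 has the survey completed each Sunday for the week just ended. With G = 7, and the survey answered on schedule, the maximum delay is 7 days, the mean is 3.5 days, and no event is more than 10 days old.

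**The case against.** A reader might infer that families are asked only monthly and that most of these events would therefore miss the protocol's 10-day limit. The documents do not support that.

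- **The limit covers few of these events.** It is the UAMS IRB's rule for UPIRTSOs. Section 8.4.1 requires such a problem to be unexpected, at least possibly related, and suggestive of greater risk than was known. Injury and shock are disclosed risks in 2.3.1, and 8.3.3.3 appears to treat events tied to equipment function as not unexpected. An unrelated hospital stay fails the relatedness test. SAEs follow 8.3.6, which has no 10-day figure, and fatal or life-threatening problems are immediate.
- **The clock may not start at the event.** For non-local events it runs from notification, and 8.4.2 does not define non-local. The trial has about 17 hospitals (10.1.4).
- **Monthly is a minimum.** Contact as needed is allowed, 1.3 permits weekly, families may volunteer events, and missed surveys prompt staff contact (7.3).
- **A majority is not shown.** It requires fewer than about 22-26% of events to be volunteered within 10 days.

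Those four points stand and set the limits of the finding. Two further points carry less weight. The yes/no lead-in on healthcare visits in 8.1 could be read as covering any visit, but the sentence before it confines the counts to respiratory symptoms. The survey form itself is not among the documents, and SAP 3.7 mentions a red-glow item that 8.1 omits, so the description in 8.1 is not the full item list. A safety item may therefore exist on the form. If so, 8.1 should say so.

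The study is also minimal risk, and broken units are to be replaced promptly. Replacement, however, depends on the site hearing of the fault.

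**Conclusion.** The point holds as a gap in safety capture. For 22 of 24 intervention weeks scheduled safety questioning has only a monthly minimum, and the weekly survey, as described, does not fill the interval for equipment-related injury, shock or malfunction or for non-respiratory hospitalization. That mismatch between 8.1 and 8.3.1 rests on no assumption about how families behave.

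The size of the delay does rest on one. Up to about two thirds (64-68%) of such events in weeks 5-26 would be more than 10 days old when first asked about if none were volunteered, and 32-34% if half were volunteered within 10 days. Both figures assume even timing of events and check-ins 28-31 days apart.

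As a deadline, 10 days matters only for problems that are UPIRTSOs, are not fatal or life-threatening, and have a clock that starts at the event. The documents do not allow that subset to be counted, so no breach rate can be stated. The change is worth making because it is cheap, not because a widespread reporting failure has been shown.

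**What to change.** Add one yes/no item to the weekly survey. It should ask whether, since the last survey, there has been any injury, shock or other problem linked to the study equipment, or any overnight hospital stay for any reason. A Yes should prompt site follow-up and the AE form. List the item in 8.1 as a survey element and in 8.3.1 and 8.3.4 as a source of AE information. If the survey form already has such an item, adding it to those sections is enough.

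In the same amendment, reconcile the weeks 5-26 check-in frequency between 5.5 and footnote 6 of 1.3, and carry the result into SAP 3.3. The IRB reporting limits need no change.

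The cost is an EDC update, an IRB amendment, a few seconds on a survey that takes 1-5 minutes and is already paid at $20, and some extra follow-up calls. No visits or staff are added.
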